5. PLANNED ANALYSES

5.1 Interim Analysis

No interim analysis has been planned.

5.2 Final Analysis

All final, planned analyses identified in this SAP will be performed by [REDACTED] Real-World Evidence Solutions (RWES) Biostatistics following [REDACTED] SOPs. Final CSR will be performed using Boehringer Ingelheim template.

6. ANALYSIS SETS

6.1 All Subjects Enrolled Set [ENR]

The all subjects enrolled (ENR) set will contain all subjects who provide informed consent for this study.

6.2 Full Analysis Set [FAS]

The full analysis set (FAS) will contain all enrolled subjects who provide informed consent for this study (ENR set) and fulfill all selection criteria. This is called “eligible patients” in the protocol.

Patients will be included in FAS if all of the following criteria are met:

1. Patients are willing and provide written informed consent prior to participate in this study
2. Patients \geq 75 years-old at the time of the study visit.
3. Patients with a diagnosis of non-valvular atrial fibrillation (NVAf).

Document:	H:\HOR-Europe\2019\2512352 - Study on anticoagulation management - BI\Proyecto\Estadistica\SAP\SAP_REBELD_version1.0_08072020.docx		
Author:	[REDACTED]	Version Number:	Version 1.0
		Version Date:	[08072020]

Template No.: RWI_TP_BIOS0013 Revision 1

Reference: RWI_WI_BIOS0015

Effective Date: 15Jun2018

4. Patients who are being treated with NOAC treatment according to the indication approved in the SmPC.
5. Patients who have started the NOAC treatment at least 3 months prior to the study visit.

Patients will be excluded from participating in this study, and will be excluded from this analysis set, if the following criterion is met:

1. Current participation in any clinical trial of a drug or device.
2. Patients who have any contraindication for NOAC treatment, according to the SmPC.

6.3 Safety Analysis Set [SAF]

The safety analysis set (SAF) will contain all enrolled subjects who receive at least one documented dose of Pradaxa®.

7. GENERAL CONSIDERATIONS

The design of the study imposes a single visit to be performed and that will coincide with one of those performed by the patients as part of routine follow-up of their disease, without interfering with usual clinical practice of the investigator.

Data will be collected through an eCRF which will include all the study variables.

Investigator will enter patient data in eCRF. Variables collected at the time of the study visit (including those related to the first NOAC initiation) will be obtained based on and limited to those available in the medical records of the selected patients. Demographic characteristics, smoking habit and alcohol consumption may be asked to the patient at the study visit if not available in the medical records. LVEF measurement will be obtained from the last images available for the patient.

Document:	H:\HOR-Europe\2019\2512352 - Study on anticoagulation management - BI\Proyecto\Estadistica\SAP\SAP_REBELD_version1.0_08072020.docx		
Author:		Version Number:	Version 1.0
		Version Date:	[08072020]

Template No.: RWI_TP_BIOS0013 Revision 1

Reference: RWI_WI_BIOS0015

Effective Date: 15Jun2018

Clinical Frailty Scale, modified EHRA scale for AF related symptoms, NYHA classification for heart failure, CHA2DS2-VASc and HAS-BLED scores will be assessed by the investigators at the study visit by evaluating the patient's functional status and medical records and the values will be directly included in the eCRF.

Final score for the Comorbidities Charlson Index will be automatically calculated based on the answers individually entered by the investigator in the eCRF for each index item (6).

Any required missing data to calculate the score for the scales or the Comorbidities Charlson Index may be asked to the patient at the study visit if not available in the medical records and should be documented, however the final score number obtained by the investigator from this information will not need to be included in medical records.

Boehringer Ingelheim reserves the right to discontinue the study overall or at a particular study site at any time for the following reasons:

1. Failure to meet expected enrolment goals overall or at a particular study site
2. Administrative reasons (i.e. study rejected by the hospital director)
3. Violation of GxP (as applicable), the study protocol, or the contract by a study site or investigator, disturbing the appropriate conduct of the study

7.1 Reference Start/End Date

Reference start date is date of study visit, collected in the eCRF as a mandatory variable.

Document:	H:\HOR-Europe\2019\2512352 - Study on anticoagulation management - BI\Proyecto\Estadistica\SAP\SAP_REBELD_version1.0_08072020.docx		
Author:	██████████	Version Number:	Version 1.0
		Version Date:	[08072020]

Template No.: RWI_TP_BIOS0013 Revision 1

Reference: RWI_WI_BIOS0015

Effective Date: 15Jun2018

7.2 Common Calculations

7.2.1 Weight

Weight (kg) will be categorized in two categories according to dose adjustment criteria in NOAC:

- ≤ 60 kg
- > 60 kg

7.2.2 Body Mass Index (BMI)

The formula to obtain Body Mass Index is the following: $BMI (kg/m^2) = \text{weight (kg)} / \text{height}^2 (m)$ and BMI will be categorized into 5 categories according to the World Health Organization (WHO):

- Underweight: $BMI < 18.5 kg/m^2$
- Normal weight: $18.5 kg/m^2 \leq BMI \leq 25 kg/m^2$
- Overweight: $25 kg/m^2 < BMI \leq 30 kg/m^2$
- Obese: $30 kg/m^2 < BMI \leq 35 kg/m^2$
- Severely Obese: $BMI > 35 kg/m^2$

7.2.3 Charlson Comorbidity Index

The Charlson Comorbidity Index (CCI) predicts the ten-year mortality for patients presenting one or more of the conditions in the model, where the age groups and each condition are awarded a specific number of points, some conditions weighing more than others, based on the adjusted risk of mortality. The more points given, the more likely the predicted adverse outcome. The index then sums the points and offers a 10-year survival/ mortality prognosis.

[https://www.thecalculator.co/health/Charlson-Comorbidity-Index-\(CCI\)-Calculator-765.html](https://www.thecalculator.co/health/Charlson-Comorbidity-Index-(CCI)-Calculator-765.html)

<https://www.mdcalc.com/charlson-comorbidity-index-cci>

Document:	H:\HOR-Europe\2019\2512352 - Study on anticoagulation management - BI\Proyecto\Estadistica\SAP\S		
	AP_REBELD_version1.0_08072020.docx		
Author:	██████████	Version Number:	Version 1.0
		Version Date:	[08072020]

Template No.: RWI_TP_BIOS0013 Revision 1

Reference: RWI_WI_BIOS0015

Effective Date: 15Jun2018

Each of the conditions listed below are awarded 1, 2, 3 or 6 points depending on the mortality risk. CCI will be calculated as the sum of all points included in the following table:

Table 2. Point assigned to Charlson Comorbidity Index

	POINTS
Age	
50–59 years	+1
60–69 years	+2
70–79 years	+3
>=80 years	+4
Myocardial infarction	+1
Congestive Heart Failure (CHF)	+1
Peripheral vascular disease	+1
Cerebrovascular Accident or Transient ischemic attack	+1
COPD	+1
Connective tissue disease	+1
Peptic ulcer disease	+1
Liver disease	
Mild	+1
Moderate to severe	+3
Diabetes mellitus	
Uncomplicated	+1
End-organ damage	+2
Hemiplegia	+2
Moderate to severe* Chronic Kidney Disease (CKD)	+2
Solid tumor	
Localized	+2
Metastatic	+6
Leukemia	+2
Lymphoma	+2
AIDS	+6

Document: H:\HOR-Europe\2019\2512352 - Study on anticoagulation management - BI\Proyecto\Estadística\SAP\SAP_REBELD_version1.0_08072020.docx

Author: [REDACTED] Version Number: Version 1.0
Version Date: [08072020]

Template No.: RWI_TP_BIOS0013 Revision 1

Reference: RWI_WI_BIOS0015

Effective Date: 15Jun2018

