Comorbidities and Clinical Risk Factors: - Heart Failure (Yes/No, New York Heart Association (NYHA) classification (24) (Refer to Annex 3); Left Ventricular Ejection Fraction, LVEF, %) - Coronary artery disease (Yes/No) - Sleep apnoea-hypopnoea syndrome (SAHS) (Yes/No) - Hypertension (Yes/No) - Comorbidity Charlson index (25) (Refer to Annex 3) (Yes/No; total score): myocardial infarction (already collected for history of thromboembolic events), congestive heart failure (already collected for the NHYA scale scoring), cerebral and peripheral vascular disease, dementia, chronic obstructive pulmonary disease, connective tissue disease, peptic ulcer disease, mild/moderate/severe liver disease, diabetes, diabetes with end-organ damage, hemiplegia, moderate/severe renal disease, any solid tumor, metastatic solid tumor, leukemia, lymphoma AIDs, age (already collected as a demographic characteristic).	x	x (NYHA classification, Charlson Index)
CHA2DS2-VAS (total score)		x
HAS-BLED(total score)		x

* Refer to [section 9.4](#) for more details about how these variables will be collected.

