9.4 DATA SOURCES

Variables collected at the time of the study visit (including those related to the time of the first NOAC initiation) will be obtained based on and limited to those available in the medical records of the selected patients.

Demographic characteristics, smoking habit and alcohol consumption may be asked to the patient at the study visit if not available in the medical records.

The variables used to determine the kidney and liver function, as well as the hemoglobin and platelet levels can be obtained from the last analytical results available in the medical charts. Creatinine clearance will be automatically determined with the serum creatinine if the Cockcroft-Gault calculation is not available in medical charts. LVEF measurement will be obtained from the last images available for the patient.

Clinical Frailty Scale (19), Modified EHRA scale for AF related symptoms (23) and NYHA classification (24) (Refer to Annex 3 for these scales), CHA2DS2-VASc, HAS-BLED scores, will be assessed by the investigators at the study visit by evaluating the patient’s functional status and medical records and the values will be directly included in the eCRF.

Final score for the Comorbidities Charlson Index (25) will be automatically calculated based on the answers individually entered by the investigator in the eCRF for each index item.

Any required missing data to calculate the score for the scales or the Comorbidities Charlson Index may be asked to the patient at the study visit if not available in the medical records and should be documented, however the final score number obtained by the investigator from this information will not need to be included in medical records.

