4.6 Changes to Analysis from Protocol

Per protocol, the variable “reason for VKA switch will be described under the OAC treatment management outcome. Finally, reason for VKA treatment switch has not been collected specifically in the VKA section of the CRF. This has been deleted from section 14.2.2 of SAP.

New analysis not included in the final protocol have been considered:

- Antiplatelet treatment according to current NOAC type
- Treatment received at the moment of thromboembolic and bleeding events.
- For all NOACs, the different doses that patients take according to HAS-BLED score.
- Underdosed and overdosed patients (for current NOAC treatment).
- HAS-BLED total score according to NOAC and antiplatelet current treatment.
- Multivariate model to evaluate the association between the Clinical Frailty Scale (dependent variable) and the thromboembolic and the bleeding events (independent variables). To calculate this analysis, only events that have occurred subsequent to the start of anticoagulant therapy (not those prior to the start of VKA / NOACs) will be considered. Univariate analysis will be performed. All variables which have a P value of less than 0.1 will be included in the multivariate analysis.

Document:	H:\HOR-Europe\2019\2512352 - Study on anticoagulation management - BI\Proyecto\Estadistica\SAP\S		
	AP_REBELD_version1.0_08072020.docx		
Author:	██████████	Version Number:	Version 1.0
		Version Date:	[08072020]

Template No.: RWI_TP_BIOS0013 Revision 1

Reference: RWI_WI_BIOS0015

Effective Date: 15Jun2018

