11.1 Derivations

Derived variables are specified in section 7.2 Common Calculations on page 18 in this SAP.

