Effective Date: 15Jun2018

		Dabigatran	Rivaroxaban	Apixaban	Edoxaban	Total	Standardized differences (Pradaxa® vs others)
	N missing						
Coronary artery disease	Valid N No Yes N missing						
Sleep apnoea-hypopnoea syndrome	Valid N No Yes N missing						
Hypertension	Valid N No Yes N missing						
Hyperlipidemia	Valid N No Yes N missing						

Table 12. Charlson Comorbidity Index according to current NOAC type

		Dabigatran	Rivaroxaban	Apixaban	Edoxaban	Total	Standardized differences (Pradaxa® vs others)
Myocardial infarction	Valid N No Yes N missing						
Congestive heart failure	Valid N No Yes N missing						
Peripheral vascular disease	Valid N No						

Document: H:\HOR-Europe\2019\2512352 - Study on anticoagulation management - BI\Proyecto\Estadistica\SAP\S AP_REBELD_version1.0_08072020.docx

Author: [REDACTED] Version Number: Version 1.0
Version Date: [08072020]

Template No.: RWI_TP_BIOS0013 Revision 1

Reference: RWI_WI_BIOS0015

Effective Date: 15Jun2018

		Dabigatran	Rivaroxaban	Apixaban	Edoxaban	Total	Standardized differences (Pradaxa® vs others)
	Yes N missing						
Cerebrovascular disease	Valid N No Yes N missing						
Dementia	Valid N No Yes N missing						
COPD	Valid N No Yes N missing						
Connective tissue disease	Valid N No Yes N missing						
Peptic ulcer disease	Valid N No Yes N missing						
Liver disease	Valid N Mild Moderate to severe N missing						
Diabetes mellitus	Valid N Uncomplicated End-organ damage N missing						
Hemiplegia	Valid N No Yes						

Document: H:\HOR-Europe\2019\2512352 - Study on anticoagulation management - BI\Proyecto\Estadística\SAP\S AP_REBELD_version1.0_08072020.docx

Author: [REDACTED]

Version Number:

Version 1.0

Version Date:

[08072020]

Template No.: RWI_TP_BIOS0013 Revision 1

Reference: RWI_WI_BIOS0015

Effective Date: 15Jun2018

		Dabigatran	Rivaroxaban	Apixaban	Edoxaban	Total	Standardized differences (Pradaxa® vs others)
	N missing						
Moderate to severe renal disease	Valid N No Yes N missing						
Solid tumor	Valid N Localized Metastatic N missing						
Leukemia	Valid N No Yes N missing						
Lymphoma	Valid N No Yes N missing						
AIDS	Valid N No Yes N missing						
Age-adjusted Charlson Comorbidity index score	Valid N Mean (SD) Median (Q1-Q3) Min-Max N missing						

Document: H:\HOR-Europe\2019\2512352 - Study on anticoagulation management - BI\Proyecto\Estadistica\SAP\S AP_REBELD_version1.0_08072020.docx

Author:

Version Number:

Version 1.0

Version Date:

[08072020]

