Effective Date: 15Jun2018

Table 20. Procedures and interventions according to duration since the first NOAC initiation

		≤4 months	>4 months	Total
Cardioversion	Valid N No Yes N missing			
Ablation	Valid N No Yes N missing			
Coronary interventions	Valid N No Yes N missing			
Type of coronary interventions	Valid N Percutaneous coronary intervention Coronary artery bypass grafting N missing			
Pacemaker carrier	Valid N No Yes N missing			

Table 21. Clinical risk factors according to duration since the first NOAC initiation

		≤4 months	>4 months	Total
Heart failure	Valid N No Yes N missing			
NYHA classification	Valid N A - No objective evidence of cardiovascular disease B - Objective evidence of minimal cardiovascular disease			

Document: H:\HOR-Europe\2019\2512352 - Study on anticoagulation management - BI\Proyecto\Estadistica\SAP\SAP_REBELD_version1.0_08072020.docx

Author: [REDACTED] Version Number: Version 1.0
Version Date: [08072020]

Template No.: RWI_TP_BIOS0013 Revision 1

Reference: RWI_WI_BIOS0015

Effective Date: 15Jun2018

		≤4 months	>4 months	Total
	C - Objective evidence of moderately severe cardiovascular disease D - Objective evidence of severe cardiovascular disease N missing			
Left ventricular ejection fraction (%)	Valid N Mean (SD) Median (Q1-Q3) Min-Max N missing			
Coronary artery disease	Valid N No Yes N missing			
Sleep apnoea-hypopnoea syndrome	Valid N No Yes N missing			
Hypertension	Valid N No Yes N missing			
Hyperlipidemia	Valid N No Yes N missing			

Table 22. Comorbidity Charlson Index according to duration since the first NOAC initiation

		≤4 months	>4 months	Total
Myocardial infarction	Valid N No Yes N missing			
Congestive heart failure	Valid N No Yes			

Document: H:\HOR-Europe\2019\2512352 - Study on anticoagulation management - BI\Proyecto\Estadística\SAP\SAP_REBELD_version1.0_08072020.docx

Author: [REDACTED] Version Number: Version 1.0
Version Date: [08072020]

Template No.: RWI_TP_BIOS0013 Revision 1

Reference: RWI_WI_BIOS0015

Effective Date: 15Jun2018

		≤4 months	>4 months	Total
	N missing			
Peripheral vascular disease	Valid N No Yes N missing			
Cerebrovascular disease	Valid N No Yes N missing			
Dementia	Valid N No Yes N missing			
COPD	Valid N No Yes N missing			
Connective tissue disease	Valid N No Yes N missing			
Peptic ulcer disease	Valid N No Yes N missing			
Liver disease	Valid N Mild Moderate to severe N missing			
Diabetes mellitus	Valid N Uncomplicated End-organ damage N missing			

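### The SAP's Charlson scoring table has no dementia row, although the protocol and the SAP's own item list and mock tables count dementia as an index item

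*SAP*

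**What the plan says.** SAP 7.2.3 defines the score by its Table 2: "CCI will be calculated as the sum of all points included in the following table". SAP 11.1 confirms that this is where the derivation lives: "Derived variables are specified in section 7.2 Common Calculations on page 18 in this SAP". In Table 2 the row for cerebrovascular accident or TIA is followed directly by COPD, and dementia does not appear elsewhere in the table.

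Four other places treat dementia as part of the index:

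- Protocol 9.3.3, Table 3 lists among the Charlson items "cerebral and peripheral vascular disease, dementia, chronic obstructive pulmonary disease".
- SAP section 11, Table 3 repeats that list.
- SAP Appendix 1, "Table 12. Charlson Comorbidity Index according to current NOAC type", has a dementia row between cerebrovascular disease and COPD, with "Age-adjusted Charlson Comorbidity index score" as its last line.
- SAP Appendix 1, "Table 22. Comorbidity Charlson Index according to duration since the first NOAC initiation", has the same rows and the same closing total.

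Protocol 9.4 describes a second route to the total, repeated in SAP section 7: it is "automatically calculated based on the answers individually entered by the investigator in the eCRF for each index item". The weights behind that automatic total are not given. SAP 4.6 does record one dropped variable, the reason for switching from VKA ("This has been deleted from section 14.2.2 of SAP"), but mentions neither dementia nor the Charlson index.

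**The concern.** A programmer following SAP 7.2.3 will sum the Table 2 points and give dementia none. Tables 12 and 22 would then show how many patients have dementia and, a few rows lower, a total that ignores it. If the eCRF total does score dementia, the study holds two different Charlson totals for the same patient, and the SAP does not say which one is analysed.

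The score has three uses. It is compared between Pradaxa and the other NOACs by a standardised difference (SAP 14.3.1, mock Table 12), the tool that protocol 9.9 names for assessing channeling. It is summarised by duration since first NOAC (mock Table 22). It is also a candidate covariate in the exploratory logistic model with frailty as the dependent variable (SAP 14.6). All patients are 75 or older, and the Clinical Frailty Scale text in protocol Annex 3 says that in people with dementia the degree of frailty corresponds to the degree of dementia. The missing item is therefore directly related to that model's outcome.

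**Working it through.** **Item count.** Conditions in SAP Table 2, taking graded conditions as one item and leaving age aside: myocardial infarction, heart failure, peripheral vascular disease, cerebrovascular accident/TIA, COPD, connective tissue disease, peptic ulcer, liver disease, diabetes, hemiplegia, chronic kidney disease, solid tumour, leukemia, lymphoma, AIDS. That is 15. Mock Tables 12 and 22 have the same 15 plus dementia, which makes 16. Dementia is the only unmatched item.

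**Maximum score.** Using the top grade of each graded item, Table 2 sums to:

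- seven 1-point conditions: 7
- hemiplegia, kidney disease, leukemia and lymphoma at 2 each: 8
- AIDS: 6
- age 4, liver 3, diabetes 2, solid tumour 6: 15

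7 + 8 + 6 + 15 = 36. With dementia at weight 1, 2, 3 or 6 the maximum would be 37, 38, 39 or 42.

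**Mean shortfall.** The documents give neither the dementia weight *w* nor its prevalence *p*, so both are assumptions. For *w* I use the values SAP 7.2.3 names for its listed conditions (1, 2, 3, 6); for *p*, 5%, 10% and 20%. Among 500 patients, 25, 50 or 100 would be under-scored. Shortfall in the mean = *w* × *p*:

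| Weight | p = 5% | p = 10% | p = 20% |
|---|---|---|---|
| 1 | 0.05 | 0.10 | 0.20 |
| 2 | 0.10 | 0.20 | 0.40 |
| 3 | 0.15 | 0.30 | 0.60 |
| 6 | 0.30 | 0.60 | 1.20 |

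**Shift in the standardised difference.** Further assumptions: prevalence differs by 5 to 10 percentage points between Pradaxa and the others, both within 5% to 20%; the SD of the score without dementia is 1.5 to 2.5; the Table 2 means are equal in the two groups; and dementia is independent of the other items. Then

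shift = *w* × (p1 − p2) / sqrt(SD² + *w*² × average of p(1 − p)).

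- Smallest case, SD 2.5, 15% v 20%. Average p(1 − p) = (0.1275 + 0.1600)/2 = 0.14375. Weight 1: 0.05/sqrt(6.25 + 0.14375) = 0.020. Weight 6: 0.30/sqrt(6.25 + 5.175) = 0.089.
- Largest case, SD 1.5, 5% v 15%. Average p(1 − p) = (0.0475 + 0.1275)/2 = 0.0875. Weight 1: 0.10/sqrt(2.25 + 0.0875) = 0.065. Weight 6: 0.60/sqrt(2.25 + 3.15) = 0.258.

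| Weight | Smallest | Largest |
|---|---|---|
| 1 | 0.020 | 0.065 |
| 2 | 0.038 | 0.124 |
| 3 | 0.055 | 0.172 |
| 6 | 0.089 | 0.258 |

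A simulation of the largest case (2,000,000 per group) gave 0.066 at weight 1 and 0.256 at weight 6, in agreement with the formula. If prevalence is the same in both groups, the shortfall cancels in the mean difference.

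**The case against.** The strongest objection is that under-scoring is conditional. Protocol 9.4 and SAP section 7 describe an automatic total from every index item, and dementia is such an item. If that total is the one analysed and it scores dementia, no patient is under-scored. This stands as a limit on the effect, but not as a defence of the text: SAP 7.2.3 would then misdescribe the derivation, and the SAP still would not say which total is used.

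The upper magnitudes are generous. SAP 7.2.3 names its weights for the conditions it lists, so they do not strictly bound a dementia weight. Within Table 2, weight 6 belongs only to metastatic tumour and AIDS, and weight 3 only to moderate-to-severe liver disease and one age band. The standardised-difference range also leaves out a zero prevalence difference, and that statistic is produced only with at least 50 patients per group. This is fair, and the weight-1 figures show how small the effect may be.

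Channeling is partly covered elsewhere. Table 12 gives dementia its own row and a standardised-difference column, so an imbalance would be visible directly. The frailty argument also cuts both ways: a Charlson covariate that includes dementia shares content with the outcome. That is a reason to decide the point openly, not to let it follow from a missing row.

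The silence of SAP 4.6 is weak evidence, because that section is not a complete log: hyperlipidemia was added and verapamil dropped from SAP Table 3 without an entry. The contradiction between Table 2 and the other four places does not depend on it.

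Finally, in the text available to me the asterisk on the kidney-disease row of Table 2 has no footnote, so something attached to the table may have been lost. The rows otherwise run in order with no gap or redaction mark, and a look at the source page settles it.

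**Conclusion.** The concern holds. SAP Table 2 is the operative scoring rule and omits an item that the protocol and the rest of the SAP count in the index. An oversight is the likelier explanation, since the SAP's own item list and mock tables keep dementia.

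The size depends on figures the documents do not give. At weight 1 the mean is 0.05 to 0.20 points too low for a prevalence of 5% to 20%, and the Pradaxa-versus-others standardised difference moves by 0.02 to 0.07 if prevalence differs by 5 to 10 points under the assumptions set out above. At weight 6 the corresponding ranges are 0.30 to 1.20 and 0.09 to 0.26. All of this applies only if the Table 2 sum is the total analysed.

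The reach is one secondary descriptive score and one exploratory candidate covariate. The primary outcome, NOAC type and dose, is untouched. It should be corrected, but it does not threaten the study's main result.

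**What to change.** - Add a dementia row to SAP Table 2, with the weight taken from the index version the SAP cites (its reference 6). SAP 7.2.3 also links two online calculators, so check that all Table 2 weights come from the same version.
- If the exclusion is intended, record and justify it in SAP 4.6 and align protocol Table 3, SAP Table 3 and mock Tables 12 and 22 with it.
- Either way, state in SAP 7.2.3 whether the SAP-derived total or the eCRF total is analysed, and list the patients in whom the two differ.

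The cost is one table row, one sentence and one cross-check listing. Dementia is already an index item in SAP Table 3 and the mock tables, so no new variable is needed.

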3.1 Primary Objectives

The primary objective is to describe the pattern of usage of NOACs prescribed according to their Summary of Product Characteristics (SmPC), by current NOAC type and dose, in elderly patients (≥ 75 years-old) with non-valvular atrial fibrillation (NVAf) at the time of the study visit.

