14.6 Exploratory analysis

History and current antiplatelet treatment will be described by current NOAC type.

Treatment received at the time of thromboembolic and bleeding events will be described, including NOAC, VKA and antiplatelet treatments.

Doses of current NOAC treatment received by the patient will be described according to HAS-BLED score (as low, intermediate and high risk).

The percentage of underdosed and overdosed patients for current NOAC treatment will be described.

HAS-BLED total score (as <3 , $3-5$, ≥ 5) will be described according to NOAC and antiplatelet current treatment.

Multivariate logistic regression will be used to evaluate the association between the Clinical Frailty Scale (dependent variable: Frailty patients - CFS scoring >4 vs Non-frailty patients - CFS scoring ≤ 4) and the thromboembolic and the bleeding events (independent variables). To calculate this analysis, only events that have occurred subsequent to the start of anticoagulant therapy (not those prior to the start of VKA / NOACs) will be considered. Other factors will be age, sex, BMI, smoking habit, alcohol consumption, time since NVAf diagnosis, NVAf type, modified EHRA scale, procedures and interventions, comorbidity Charlson index and clinical risk factors. Univariate analysis will be performed. All variables which have a P value of less than 0.1 will be included in the multivariate analysis.

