	Apixaban (Serum creatinine $< 1,5$ mg/dl or creatinine clearance ≥ 30 mL/min)			NA
	Apixaban (Serum creatinine $\geq 1,5$ mg/dl or creatinine clearance < 30 mL/min)		NA	
Edoxaban	Edoxaban (Body weight > 60 kg)			NA
	Edoxaban (Body weight ≤ 60 kg)		NA	
	Edoxaban (creatinine clearance > 50 mL/min)			NA
	Edoxaban (creatinine clearance 15-50 mL/min)		NA	

Table 52. HAS-BLED score according NOAC+antiplatelet current treatment

		HAS-BLED score				
		Valid N	< 3	3-5	≥ 5	N missing
Current treatment	Dabigatran+aspirin					
	Dabigatran+clopidogrel					
	Dabigatran+peasugrel					
	...					
	... (for all combinations)					

Row percentage will be calculated

Document: H:\HOR-Europe\2019\2512352 - Study on anticoagulation management - BI\Proyecto\Estadistica\SAP\S AP_REBELD_version1.0_08072020.docx

Author: [REDACTED]

Version Number:

Version 1.0

Version Date:

[08072020]

Template No.: RWI_TP_BIOS0013 Revision 1

Reference: RWI_WI_BIOS0015

Effective Date: 15Jun2018

Table 53. Multivariate logistic model to evaluate the association between the Clinical Frailty Scale and the thromboembolic and the bleeding events

Variable	Estimate	Standard error	t-value	Pr> t	OR

*dependent variable: CFS in two categories: Frailty patients - CFS scoring >4 vs Non-frailty patients - CFS scoring ≤4)

*independent variables: thromboembolic and bleeding events. Other factors will be age, sex, BMI, smoking habit, alcohol consumption, time since NVAF diagnosis, NVAF type, modified EHRA scale, procedures and interventions, comorbidity Charlson index and clinical risk factors. Univariate analysis will be performed and all variables which have a P value of less than 0.1 will be included in the multivariate analysis.

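### The Charlson index offered to the exploratory frailty model already contains age points, so if age and the index both enter, the printed age odds ratio is not the comorbidity-adjusted one

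*SAP*

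**What the plan says.** SAP 7.2.3 describes an index "where the age groups and each condition are awarded a specific number of points" and then states that "CCI will be calculated as the sum of all points included in the following table". The first rows of that table (SAP Table 2) are age bands: +1 at 50-59, +2 at 60-69, +3 at 70-79 and +4 at 80 or over. Tables 12 and 22 carry the result under the label "Age-adjusted Charlson Comorbidity index score". The SAP defines no version without the age rows.

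SAP 14.6 plans a logistic regression with a binary outcome ("dependent variable: Frailty patients - CFS scoring >4 vs Non-frailty patients - CFS scoring ≤ 4"). The factors of interest are thromboembolic and bleeding events. For adjustment it says "Other factors will be age, sex, BMI, smoking habit, alcohol consumption", and the list goes on to the Charlson index. The Table 53 footnote repeats the list, including "procedures and interventions, comorbidity Charlson index and clinical risk factors". Entry is by screening: "All variables which have a P value of less than 0.1 will be included in the multivariate analysis". Neither age nor the index is forced in, and 14.6 does not say whether age is continuous or grouped. SAP 8.5 and 14.1.1 group age as 75-79, 80-84 and 85 or over for subgroup tables. Table 53 prints an estimate, standard error, P value and odds ratio for each variable.

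**The concern.** A programmer following the SAP would offer the model age and an index that includes age. If both are selected, the age coefficient describes older against younger patients at the same age-inclusive score. Across the boundary at 80, holding that score fixed means comparing an older patient with a younger one who has one more comorbidity point. A reader of Table 53 would not normally take the age odds ratio to mean that. Read as the effect of age adjusted for comorbidity, it could be too small and could look non-significant for a reason of scoring alone.

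The stakes are limited. Age is an adjustment factor in one exploratory analysis added after the protocol, and no primary or secondary objective uses its odds ratio.

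**Working it through.** The documents give no coefficient, odds ratio or power for this model, so there is no planned figure to reproduce. The check is algebra, followed by simulation under stated assumptions.

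**Inputs from the documents.** All patients are 75 or older (SAP 3.1), so the age points A are 3 (75-79) or 4 (80 or over). About 500 patients are planned (SAP 4.2).

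**Algebra.** Let C be the comorbidity points and T = C + A the index as defined. Suppose logit(frail) = b0 + b_age × age + b_c × C. Substituting C = T − A gives

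logit(frail) = b0 + [b_age × age − b_c × A] + b_c × T.

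The age term absorbs −b_c × A.

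- *Grouped age (75-79, 80-84, 85 or over).* A is constant within groups, so this is an exact reparameterisation. Each age odds ratio against 75-79 is divided by exp(b_c), the odds ratio per Charlson point. Fit and Charlson coefficient are unchanged.
- *Linear age.* The step at 80 is not linear, so the result is approximate: the log odds ratio per year falls by about b_c × s, where s is the slope of A on age.

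**Large-sample check.** Assumed, not in the documents: 200,000 patients, mean age 82 (SD 4.6), 60% aged 80 or over, comorbidity points Poisson with mean 2, independent of age. Then s = 0.0749. For an age odds ratio of 1.10 per year and 1.25 per Charlson point: ln 1.10 − 0.0749 × ln 1.25 = 0.0953 − 0.0167 = 0.0786, an odds ratio of 1.082. The fitted value was 1.083. Fitted odds ratios per year for an assumed age odds ratio of 1.10:

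| Assumed odds ratio per Charlson point | Index without age points | Index as planned |
|---|---|---|
| 0.9 | 1.100 | 1.108 |
| 1.0 | 1.099 | 1.099 |
| 1.1 | 1.100 | 1.093 |
| 1.25 | 1.099 | 1.083 |
| 1.5 | 1.101 | 1.071 |
| 2.0 | 1.101 | 1.050 |

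With grouped age and an assumed 1.25 per point, 80-84 against 75-79 went from 1.51 to 1.22, and 85 or over from 2.82 to 2.28. The fitted ratio between the two versions was 1.240, equal to the fitted Charlson odds ratio, and the log-likelihoods were identical.

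**At the planned size.** 400 data sets of 500 patients per scenario, linear age. Assumed: 34% frail, mean age 80.6, half aged 80 or over, Poisson comorbidity points with mean 2.2, an event term in the model. Mean age coefficients:

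| True age effect per year | True effect per Charlson point | Planned | Without age points | Share lost |
|---|---|---|---|---|
| 0.05 | 0.35 | 0.022 | 0.051 | 1 − 0.022/0.051 = 57% |
| 0.05 | 0.20 | 0.032 | 0.048 | 1 − 0.032/0.048 = 33% |
| 0.10 | 0.35 | 0.073 | 0.102 | 1 − 0.073/0.102 = 28% |
| 0.10 | 0.20 | 0.084 | 0.100 | 1 − 0.084/0.100 = 16% |

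A separate set with slightly different assumptions (35% frail, mean age about 81) gave 0.025 against 0.052 and 0.087 against 0.103 at the extremes, losses of 51.9% and 15.5%. Hence the range of about 15-57%.

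**Screening and significance.** Both factors passed P<0.1 in 68-99.5% of data sets, depending on the scenario. In the first row, the chance that age reached P<0.05 fell from 64% to 15% over all data sets, and from 88% to 21% among those where both passed. With a stronger age effect the loss is small: at 1.10 per year and 1.25 per point, 1,000 data sets of 500 gave 99.6% against 96.8%.

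**Other coefficients.** With a true Charlson coefficient of 0.35, the planned model gave 0.333 and the corrected one 0.350. As odds ratios, large-sample runs gave 1.40 against 1.42, and 1.21 against 1.22 for a true coefficient of 0.2. With events simulated independently of the index, the event odds ratio was 1.823 against 1.824.

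**The case against.** The strongest reply is that nothing is mis-estimated. With the age groups that the SAP uses elsewhere, the two models are the same model: same likelihood, same predictions, same Charlson coefficient. The age odds ratio merely answers a different conditional question, and the 75-year limit caps the overlap at one point. Age within the index is also deliberate: protocol Table 3 and SAP Table 3 list it as a Charlson item, and the output tables label the score as age-adjusted. Finally, the model exists to examine events, not age. All of this stands, and it makes the point minor. It does not remove it, because Table 53 prints the age odds ratio and P value, and nothing tells the reader which conditional question they answer.

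Several stronger readings are tempting and are not supported.

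- *The age odds ratio will be too small.* This needs both terms to pass the screen and a positive Charlson coefficient. That sign is plausible for frailty, but the documents do not give it. At zero nothing changes, and below zero the age odds ratio is too large (1.108 against 1.100 in the table).
- *The Charlson odds ratio is no longer a comorbidity effect.* It moves by about 0.02 or less in the scenarios with 0.2-0.35 per point.
- *More than half of the age effect disappears.* That is the most adverse of four assumed pairs; the mildest loses about 16%.
- *The event odds ratios are distorted by the age points.* They were not in these simulations, but there the events were independent of the index. In the study, myocardial infarction and stroke or TIA are both Charlson items and thromboembolic events. That overlap is a separate matter, which removing the age rows does not settle.

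**Conclusion.** The point holds in a conditional form and is a minor, inexpensive improvement. The plan defines only an age-inclusive Charlson score and offers it to the frailty model beside age. If both are selected, the age odds ratio is not the comorbidity-adjusted one unless the Charlson coefficient is zero, and it is smaller when that coefficient is positive.

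The size is not fixed by the documents. The 15-57% range for linear age rests on the assumed effects, age distribution, comorbidity distribution and frailty prevalence given above. The division of grouped age odds ratios by the odds ratio per Charlson point is exact algebra, but that odds ratio is itself unknown. The finding does not touch the primary or secondary objectives.

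**What to change.** In SAP 14.6 and the Table 53 footnote, replace the Charlson index with the Charlson comorbidity points, that is, the sum over SAP Table 2 without the age rows. Keep age as its own candidate factor and state how it is coded (per year, or in the groups of SAP 8.5). The P<0.1 screen then applies to the comorbidity-only score. The age-adjusted index can stay as it is in Tables 12 and 22.

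The cost is a sentence in the SAP, a matching footnote edit and one derived variable. The Charlson items are entered individually in the eCRF (SAP section 7), so no new data are needed and nothing is lost.
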